Hypothesis 1b: Time periods during which clinics are randomly assigned to receive the modified imaging reports will have a lower rate of subsequent opioid prescriptions than time periods during which clinics do not receive modified reports.

Aim 1c: To determine if inserting epidemiological evidence decreases subsequent cross-sectional imaging magnetic resonance (MR) and computed tomography (CT).

Hypothesis 1c: Time periods during which randomly assigned clinics receive modified imaging reports will have a lower rate of subsequent cross-sectional imaging than time periods for which clinics do not.

Aim 1d: To explore whether adding epidemiological evidence decreases overall costs of care for low back pain based on CMS reimbursement.

Hypothesis 1d: Clinics that are randomly assigned to receive the modified imaging reports will have lower back pain-related estimated payer costs than clinics whose patients do not receive modified reports. Costs are another outcome that are highly relevant to both patients and health systems.

Aim 2: To determine whether inserting age-specific prevalence of imaging findings in asymptomatic subjects has a differential effect on subsequent back-related interventions if inserted into lumbar spine MR and CT imaging reports compared with plain films.

Hypothesis 2: Inserting epidemiological information into plain film reports will result in a greater decrease in subsequent back-related interventions than similar information put into MR and CT reports. Given that plain films are generally obtained earlier in the course of back pain and more frequently than MR and CT, the potential impact of inserting epidemiological information into plain film reports is large.

Aim 3: To determine if specific imaging findings influence subsequent interventions.

Hypothesis 3: Inserting the statement will result in a greater decrease in subsequent interventions for patients without clinically important findings compared with patients who have clinically important imaging findings. Our work and others have shown that certain imaging findings are likely to be clinically more important than others (e.g. nerve root compression, moderate to severe central stenosis, disc extrusions). We expect that patients without these more important findings will have a greater reduction in subsequent interventions.

4. Study Details

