- Participating patient representatives were provided with a sample radiology report and four different versions of the intervention macro. They were asked the following questions:

- What is your age?
- Have you ever sought medical care for low back pain?
- Which format option did you prefer?
- Why did you prefer that format option over the others?
- Based on this information, would you say disc degeneration is common or rare?
- What is clear about the information presented?
- What is confusing about the information presented?
- How would you use the information presented in the option that you preferred?
- If you received a radiology report with the information in the option that you preferred, would you feel less or more concerned about having the imaging finding(s) that are common in people without back pain? For example, would you feel less or more concerned about having a degenerated disk?

10. On-line survey with seven primary care physicians for feedback and comment. Participating providers were provided with a sample radiology report and three different versions of the intervention macro. They were asked the following questions:

- What proportion of your patient visits are related to low back pain?
- Which format option do you prefer?
- Why did you prefer that format option over the others?
- Based on this information, would you say disc degeneration is common or rare?
- What could be improved about your preferred option?
- If you received a radiology report with the information in the option that you preferred, would you be less or more concerned about a given patient's imaging finding? For example, would you feel less or more concerned about a patient having a degenerated disk?
- How would the information presented in the option that you preferred inform your clinical decision making?

The final text is a product of the efforts described above and will serve as the final intervention. Different wording is offered based on 1) Age (<40, 40-60, and >60 years of age) and 2) Modality (plain film, CT, MR).

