Hypothesis 1d: Clinics that are randomly assigned to receive the modified imaging reports will have lower back pain-related estimated payer costs than clinics whose patients do not receive modified reports.

We will apply CMS-based reimbursement amounts to RVU calculations in order to standardize unit cost estimation among our sites. We will use CPT and diagnostic codes to determine whether interventions are associated with back pain, and multiply the total back-treatment related RVUs at sites by the unit price payment amounts for respective RVU calculations.

Table 5: Sample of RVUs and CMS-based payment amounts for lumbar imaging (US\$ 2012)

CPT	Diagnostic Imaging Exam	Hospital (facility)		Professional		
		Hosp RVU	Hosp payment	Pro wRVU	Pro tRVU	Pro payment
72100	2 view x-ray exam lower	0.6399	\$48.22	0.22	0.34	\$12.08

	spine					
	4 view x-ray exam lower					
72120	spine	0.6399	\$48.22	0.22	0.35	\$12.47
72131	CT lumbar spine w/o dye	2.746	\$206.54	1	1.44	\$51.57
72132	CT lumbar spine w/dye	4.2918	\$323.42	1.22	1.75	\$62.58
72133	CT lumbar spine w/o & w/dye	4.7716	\$359.59	1.27	1.82	\$65.10
72148	MRI lumbar spine w/o dye	4.8333	\$364.24	1.48	2.14	\$76.44
72149	MRI lumbar spine w/dye	6.2248	\$469.10	1.78	2.57	\$91.88
72158	MRI lumbar spine w/o & w/dye	7.6273	\$574.79	2.36	3.41	\$121.79

Aim 2: To determine whether inserting age-specific prevalence of imaging findings in asymptomatic subjects has a differential effect on subsequent back-related interventions if inserted into lumbar spine magnetic resonance (MR) and computed tomography (CT) imaging reports compared with plain films.

Hypothesis 2: Inserting epidemiological information into plain film reports will result in a greater decrease in subsequent back-related interventions than similar information put into MR and CT reports.

Our pilot work examined only MR. However, given that plain films are generally obtained earlier in the course of back pain and more frequently than cross-sectional imaging, the potential impact of inserting epidemiological information into plain film reports is large. In each separate analysis of Aim 1 outcomes, we will add an indicator of imaging modality (plain film versus MR versus CT) and an imaging modality by treatment interaction term in the model. Primary inference will be on the interaction term, where we expect that patients with more advanced imaging will have a significantly greater reduction in subsequent interventions than those who receive a plain film image.

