**Primary Analysis:** The primary longitudinal model for back pain specific RVUs will use a time-varying intervention status indicator  $Status_{kt}$  (0 = control, 1 = intervention, for clinic  $k$  at time  $t$ ). Use of the time-dependent intervention status indicator permits both within-clinic contrasts that inform intervention effects (post-versus pre-intervention) as well as contrasts across clinics with different intervention statuses within each time period. The specific regression model will adopt a functional form given below, with fixed effects for time (linear), age (18-39, 40-59, 60+, using two dummy variables), imaging modality type (plain film, CT, MRI using two dummy variables), and clinic size (small, medium, large, using two dummy variables), and site (Group Health Cooperative, Henry Ford, Kaiser Permanente, Mayo Clinic, using three dummy variables) in addition to random

Lumbar Imaging Reporting with Epidemiology (LIRE)  
 STATISTICAL ANALYSIS PLAN

effects for provider, clinic, and intervention status:

[figure not shown]
$$Y_{ijk} = \beta_0 + \beta_1 \cdot Time_t + \beta_2^T \cdot Age_{ijk} + \beta_3^T \cdot Modality_{ijk} + \beta_4^T \cdot Size_k + \beta_5^T \cdot Site_k + \lambda_0 \cdot Status_{kt} + \quad \text{mean model}$$

$$b_{k,0} + b_{k,1} \cdot Status_{kt} + \quad \text{clinic random effects}$$

$$a_{jk,0} + e_{ijk} \quad \text{provider random effects and errors}$$

We will collect the outcome measure  $Y_{ijk}$  on patient  $i$  ( $i=1,2,\dots,n_j$ ) under primary care provider  $j$  ( $j=1,2,\dots,n_k$ ) enrolled in time period  $t$  ( $t=0,1,2,\dots,5$ ) in order to evaluate the overall effect of the intervention at the level of the clinic  $k$  ( $k=1,2,\dots,110$ ). Note that we will collect a single outcome measure for each subject recording the total utilization (RVU) over the 12 months after the index imaging event. Given that the random effects structure may contain additional elements (see below) we will use a robust standard error to test the null hypothesis that  $\lambda_0 = 0$ . For example, using SAS PROC MIXED we can use the “empirical” option in order to obtain robust standard errors. Alternatively, use of the jackknife (at the clinic level) provides a robust standard error estimate (if using R and *lmer*) that is simple to compute.

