**Analysis for Aim 2:** The hypothesis of Aim 2 is that there will be a differential effect of the intervention according to the imaging modality used. In order to test this hypothesis we will analyze patient-level data according to the appropriate LMM or GLMM given above, but including the interactions between  $Modality_{ijk}$  indicators (modeled using two indicator variables coding CT and MR, with plain film as the reference) and  $Status_{kt}$ . A test of the interaction terms (2 degree of freedom Wald test) will be used to test the null hypothesis that the effect of the intervention does not vary according the imaging modality.

**Analysis for Aim 3:** The hypothesis of Aim 3 is that there will be a differential effect of the intervention according to the results that are found in the imaging report. We will use an additional variable,  $ImageFinding_{ijk}$ , that takes the value 1 if a significant image finding is present, and 0 otherwise (see detail regarding variable specification in protocol). We will test the null hypothesis that the interaction between  $ImageFinding_{ijk}$  and  $Status_{kt}$  is zero using a Wald test.

[figure not shown]
**Power Calculations:** Our UH2 efforts with respect to sample size and statistical power focused on two key items. First, an important aim of our UH2 Working Group 2 was to obtain an accurate clinic and provider count for each health system. We will now randomize  $n=110$  clinics (1,824 PCPs), which is slightly lower than the  $n=128$  clinics (1,898 PCPs) assumed in our initial project application. However, the majority of the clinics that were dropped were those with only one PCP and therefore would not have contributed much information to the analysis. Second, in our Working Group 3 we sought to develop and characterize a composite RVU summary to be used as the primary outcome measure in this study. In our UH2 project application we discussed statistical power in the context of an important secondary outcome measure, a reduction in subsequent opioid prescription rates. We now present statistical power for the primary outcome measure using data from the BOLD Registry to inform key design parameter estimates.

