**Lumbar Imaging with Reporting of Epidemiology (LIRE) Statistical Analysis Plan Revisions**

The following table includes amendments to our statistical analysis plan (SAP) that we included in statistical models for the manuscript but that we did not specify in our original SAP.

Amendments to Statistical Analysis Plan (SAP)	
Number of clinics	

 
• 110 to 98 clinics
 
	When we wrote the SAP we estimated that we would have 110 clinics participating in the trial. We dropped ten clinics prior to randomization for logistical reasons. We dropped two additional small clinics just after randomization and before the first data submission: one had closed and the other had been subsumed in another clinic.
Covariates	We made all decisions regarding covariates before we began the statistical analysis.
Covariates added	Rationale

 
• Site by time interactions
 
	Allow for differential time trends by site

 
• Gender
 
	Allow for outcome differences by gender (precision)

 
• Charlson Comorbidity Index category
 
	Comorbidity measures are associated with outcomes. We sought greater precision by including this general measure of health.

 
• Prior opioid status (opioid models only)
 
	Allow for differences in outcome between those without and those with prior opioid prescriptions (precision)
Covariates transformed	

 
• Time
 
	The SAP and protocol paper indicated that we would model time linearly as 6-month time period (t = 0, 1, 2, 3, 4, 5). Upon further thought, we decided that a more granular measure (i.e. day) would be more appropriate.

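### The Aim 2 models let the intervention effect vary by imaging modality only, so a difference in effect by age or stage of illness can appear as a modality effect; a sensitivity analysis and careful wording would address this.

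*Protocol*

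**What the plan says.** **The question.** Protocol section 3 (Aim 2) and the SAP's Research Aims ask about the effect of placing the text in MR and CT reports compared with plain film reports. The rationale under Hypothesis 2 refers to when each test is ordered: "Given that plain films are generally obtained earlier in the course of back pain and more frequently than MR and CT". Protocol 5.7 repeats the point.

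**The intervention.** The final text is not uniform. Protocol 5.6 (Working Group 1 progress) states: "Different wording is offered based on 1) Age (<40, 40-60, and >60 years of age) and 2) Modality (plain film, CT, MR".

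**The model.** For Aim 2, Protocol 5.7 says "we will add an indicator of imaging modality (plain film versus MR versus CT) and an imaging modality by treatment interaction term in the model", and makes that term the primary inference. The SAP (Analysis for Aim 2) agrees: "we will analyze patient-level data according to the appropriate LMM or GLMM given above, but including the interactions between" the modality indicators and intervention status. It continues: "A test of the interaction terms (2 degree of freedom Wald test) will be used to test the null hypothesis". In the SAP's Primary Analysis, age enters as "age (18-39, 40-59, 60+, using two dummy variables", among the fixed main effects. The SAP revisions add site-by-time terms, gender, Charlson category and "Prior opioid status (opioid models only"; none is listed as interacting with intervention status. Finding type interacts with status, but in the separate Aim 3 model.

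**Opioids.** Protocol 5.7 (Aim 1b) also plans separate opioid analyses for patients with and without an active prescription at baseline.

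**The concern.** Clinics are randomised to a start date. Nobody is randomised to a plain film, CT or MR; the primary care provider orders the test. Patients with different index modalities can therefore differ in age, stage and indication. A main effect for age removes age differences in the outcome, but not age differences in how much the text changes the outcome. With only modality allowed to modify the effect, any such difference that is unevenly spread over modalities goes into the modality-by-status coefficient.

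What is at stake is the reading of Aim 2. That the text works better in plain film reports and that it works better in patients early in their course are different conclusions. The error can also run the other way, with an opposing age or stage pattern hiding a real modality difference. The expected direction gives no safeguard: in Protocol 5.7 the hypothesis favours plain film and the analysis paragraph favours advanced imaging, so either sign could be called expected.

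**Working it through.** The documents give no power, effect size or sample size for Aim 2, so there is no planned figure to reproduce. What follows is an illustration of size.

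**Inputs from the documents.** Residual variance of log(RVU + 1) is 1.230 (SAP, Power for Primary Outcome). About 100,000 patients are expected (Protocol, human subjects section). The reference effect is a 5% reduction in median RVU (SAP, same place).

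**Assumed inputs, because the documents give none.** MR/CT share 20 to 30%. Half of patients are under intervention in each modality. Age mixes (youngest/middle/oldest band) run from close to far apart. There is no true modality effect.

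**Step 1: spurious difference from age.** Formula: sum over age bands of (effect in band) × (plain film share − MR/CT share).
- Close mixes: plain film 20/40/40%, MR/CT 22/43/35%, reductions of 8, 4 and 0%. Result: 8(−0.02) + 4(−0.03) + 0(0.05) = −0.28, about 0.3 points.
- Distant mixes: plain film 15/35/50%, MR/CT 25/45/30%, reductions of 10, 5 and 0%. Result: 10(−0.10) + 5(−0.10) + 0(0.20) = −1.5 points.

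Reversing the age gradient or the mixes reverses the sign and leaves the size unchanged.

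**Step 2: standard error of the interaction.** SE = √[1.23 × (2/(N_PF/2) + 2/(N_MRCT/2))].
- 20% MR/CT: √[1.23 × (2/40,000 + 2/10,000)] = 0.0175.
- 30% MR/CT: √[1.23 × (2/35,000 + 2/15,000)] = 0.0153.

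**Step 3: rejection rate at a nominal 5%.** Percentage points are treated as log units × 100.
- Smallest case: 0.28/1.75 = 0.16 SE, giving 5.3% with 1 degree of freedom.
- Largest case: 1.5/1.53 = 0.98 SE, giving 16.5% with 1 degree of freedom.
- For the planned 2-degree-of-freedom Wald test, with the same noncentrality (0.98² = 0.96 at the top), the range is 5.2 to 12.9%.

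**Step 4: larger imbalances and the effect of the remedy.** A simulation used 100,000 patients, 110 clinics, six periods and modality shares of 75/5/20% for plain film, CT and MR. The older or later-stage share was 35% in plain film and higher in CT and MR by the imbalance shown. The text acted only in the younger or earlier-stage group. The model had clinic fixed effects and model-based standard errors, a simplification of the SAP's mixed model with robust errors. There were 150 runs per row. The expected spurious MR coefficient is −log(1 − effect) × imbalance; for example, 0.0513 × 0.40 = 0.021.

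| Effect in the responsive group | Imbalance (points) | Expected spurious MR coefficient | 2-df rejection, planned model | 2-df rejection, modifier × status added |
|---|---|---|---|---|
| 5% | 10 | 0.005 | 5% | 6% |
| 5% | 20 | 0.010 | 7% | 3% |
| 5% | 30 | 0.015 | 18% | 2% |
| 5% | 40 | 0.021 | 20% | 7% |
| 10% | 10 | 0.011 | 11% | 2% |
| 10% | 20 | 0.021 | 16% | 6% |
| 10% | 30 | 0.032 | 38% | 6% |
| 10% | 40 | 0.042 | 68% | 3% |

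With 150 runs, a true 5% rate has a simulation standard error of √(0.05 × 0.95/150) = 1.8 points, so the last column is compatible with 5%. With no imbalance the expected bias is zero even when the term is omitted. Adding the term brought the mean MR coefficient to within 0.003 of zero. Its standard error rose from 0.0177 to at most 0.0187, which is 0.0187/0.0177 = 1.06, or about 6%.

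**The case against.** The strongest reply is that the planned test is right for the question the SAP states, namely that "there will be a differential effect of the intervention according to the imaging modality used". That is effect modification, and within each modality the comparison of intervention with control rests on clinic randomisation. This stands. A reader might infer that the Aim 2 test is invalid or its result necessarily biased; the documents do not support that. The difficulty begins only when a difference is credited to the report type, a reading that the wording of Aim 2 invites.

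Second, earlier timing is part of the stated rationale, so adjusting for stage would remove some of the hypothesised mechanism. This also stands. It is a reason to report the interaction both with and without the extra terms and to let neither replace the other.

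Third, the age argument is inferred. A reader might take Protocol Table 3 as proof that the effect must vary with age, since disc degeneration rises from 77% under 45 to 100% over 65. But protrusion (29, 34, 31 and 35% across the age groups) and annular tear (39, 36, 37 and 41%) are nearly flat, and both kinds of finding appear in the example text. No section gives age by modality or states an expected age-varying effect.

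Fourth, prior opioid use is not ignored as a possible modifier: the stratified opioid analysis under Aim 1b covers it for that outcome. It is not carried into Aim 2 for RVUs or re-imaging.

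Finally, in Steps 1 to 3 every assumed bias is smaller than the interaction's standard error, and the high rates in Step 4 need a 10% effect confined to one group, twice the SAP's reference effect, with 30- to 40-point imbalances.

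**Conclusion.** The concern holds in a conditional form. The Aim 2 model has no interaction of intervention status with age or with any marker of stage, so the modality interaction can absorb such differences. Two conditions are needed: an effect that varies with age or stage, and a mix that differs by modality. The documents support the second for stage, without a size, and are silent on it for age.

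The size is therefore unknown. Under the modest assumed age mixes, the false rejection rate is about 5 to 13% for the planned test (5 to 17% with 1 degree of freedom), which at the low end is essentially no inflation. It reaches 20% or 68% only at a 40-point imbalance with a 5% or 10% effect in one group.

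A further tempting reading is that an interaction which survives adjustment would show that report type matters. It would not: no listed covariate measures stage or duration of pain, or the indication for the test, and prior opioid status is an imperfect stand-in. Aim 1 is unaffected. This is a cheap improvement to a secondary aim, not a flaw in the main analysis.

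**What to change.** 1. Keep the planned 2-degree-of-freedom modality test as it is.
2. Prespecify a sensitivity analysis for each Aim 2 outcome that adds status × age band and status × prior opioid status, each with its main effect. Prior opioid status is already collected for the opioid models; for the opioid outcome this complements the planned stratified analysis. The model's age bands can serve: they depart from the 5.6 text bands only in where age 60 falls.
3. Report the modality interaction with and without these terms, and tabulate age band and prior opioid status by modality so that the imbalance can be seen.
4. Describe the Aim 2 result as a difference in effect between patients imaged by each modality. Do not attribute it to report type itself, even if the interaction remains.

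The cost is a few parameters, an extra table row for the sensitivity result, a short descriptive table and a slightly wider interval for the modality interaction (about 6% at most in the simulated cases, with one two-level modifier). No new data are needed.

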4.1 Eligibility Criteria

Because this is a pragmatic trial, we have minimized eligibility restrictions, making the inclusion criteria as broad as possible. Clinics will be the primary unit of randomization and analysis, while the intervention will be applied at the individual patient level. Thus two sets of eligibility criteria are necessary: clinic and patient.

The criteria for *clinic eligibility* are that the health care providers are a distinct, readily identifiable group that has at least a subgroup of primary care providers who do not practice at another clinic that will also be part of the trial. This requirement of being based primarily at one site is to minimize cross-contamination (having the use of epidemiological benchmarks at one site influence another site not receiving the benchmarks).

The criteria for *patient eligibility* are that they have had an imaging study of the lumbar spine requested by a primary care provider. We will include all conventional lumbar spine imaging (plain films, CT, MR) ordered by primary caregivers.

